## 12.0 Data Management

### Sample size, Statistical Power and Analysis

Sample size justification. As the study is designed to demonstrate feasibility, sample size was determined based on pragmatic considerations, rather than formal power analysis. The study plans to enroll 60 PLWH randomized to CPT-L or Lifesteps. This sample size is adequate to assess feasibility outcomes (enrollment, attrition, retention, adherence to protocol and fidelity). The sample size recruited during our recruitment period (18 months) will allow the team to specifically justify that we can approach a reasonable sample for a larger RCT in an expanded recruitment period. Further, with a target retention rate of ≥90%, an enrolled sample of 60 participants produces a 95% confidence interval from 82% to 98% and an adherence rate of 80% will produce a 95% confidence interval between 70% and 90%. The study will produce both within and between treatment group estimates of visit attendance (yes/no), ART adherence (85% of doses taken), and proportion of detectable viral load (yes/no). Further, if mean HIV Symptom Severity, CD4 cell counts, PCL and CAPS-5 scores will be assessed post-intervention and a sample of 30 participants in each group will provide adequate power to determine estimated a confidence interval with a difference of ½ a standard deviation (0.51 SD) of the between group mean estimate. If the difference in proportion of participants with detectable viral load is 10% in the CPT group and 20% in the SOC Lifesteps group at the close of treatment (10% difference), the sample of 30 participants in each study group will provide an 18% confidence interval on either side of the estimated difference.

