In addition to feasibility, efficacy and adherence outcomes will aid in development of the subsequent R01. Parameter and variability estimates of efficacy outcomes will be derived from appropriate statistical models. Specifically, HIV symptom distress (physical and mental), CD4 cell counts, viral load, clinic attendance and ART adherence will be measured at pre- and post-intervention and 3-month follow-up. Proportion of participants with Clinic attendance (yes/no), ART adherence (yes/no), and detectable viral load at the end of treatment and follow up will be compared between study groups using a modified Poisson regression approach with a robust sandwich variance estimator. Initial analytic models for binary outcomes will include the primary treatment effect, study visit and interaction of study visit and treatment as well as variables used to balance the randomization procedure. Adjusted models will explore the additional baseline covariates significantly associated with outcomes. The proportion successful in each treatment group at each visit, the relative risk of success and associated 95% confidence interval will be reported. We anticipate that treatment will decrease CD4 cell counts and HIV

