Exploratory Investigation into Moderators and Mediators. Baseline measures of sex and gender identity as well as history of viral suppression will be assessed as treatment moderators of feasibility, HIV and PTSD outcomes. Moderation will be assessed utilizing addition of interactions into models described above. Although not specifically powered to detect statistically significant interactions, interaction and stratified effect sizes will be presented. Effect sizes will inform relevant hypothesis for future R01 study development. We hypothesize that changes in PTSD-related avoidant coping following the intervention will mediate the relationship between treatment and HIV outcomes at follow up (CD4 Cell Counts, HIV Symptom Severity, ART adherence). Mediation models will estimate indirect and direct effects as well as the proportion mediated using the PROCESS macro. Bootstrap resamples (1000 resamples) will provide point estimates and confidence intervals of the mediating effect of changes in avoidant coping on the relationship between treatment with CPT-L and HIV related outcomes. Feasibility for the subsequent R01 is needed to demonstrate that data can be successfully collected to analyze proposed efficacy and mechanism testing hypotheses (see Form F for Proposed RCT analyses).

Data Capture and Management. This study will use Research Electronic Data Capture (REDCap) for data capture and management. REDCap is a software toolset and workflow methodology for the electronic collection and management of research and clinical trials data. REDCap provides secure, web-based, flexible applications, including real-time validation rules with automated data type and range checks at the time of data entry. Exports are made available for several statistical packages including SPSS, SAS, SATA, R and Microsoft Excel. The study-specific REDCap database will be designed and developed by MUSC research team. The provision of REDCap is made available through the South Carolina Clinical & Translational Research (SCTR) Institute at MUSC with NIH Grant awards UL1RR029882 and UL1TR000062. The recruitment report will be stored in REDCap but will be separate from the research database. Only IRB approved study personnel will have access to the recruitment report. The study team will lose access to the recruitment project at the conclusion of enrollment. The recruitment REDcap will contain both identifiers and health information in the same project.

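### The exploratory mediation plan reports a proportion mediated with no formula, no scale for ART adherence and no rule for a near-zero total effect; at 48 to 60 participants the ratio is unstable unless the total effect is large

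*Combined protocol and SAP*

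**What the plan says.** In section 12.0, the paragraph on exploratory moderators and mediators hypothesises that change in PTSD-related avoidant coping mediates the effect of treatment on CD4 count, HIV symptom severity and ART adherence at follow-up. It then commits to three quantities: "Mediation models will estimate indirect and direct effects as well as the proportion mediated using the PROCESS macro". On uncertainty it adds: "Bootstrap resamples (1000 resamples) will provide point estimates and confidence intervals of the mediating effect". It does not say whether the proportion itself gets an interval.

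The paragraph gives no formula for the proportion, no link function, no scale for ART adherence, no mediation effect size, and no instruction for a total effect close to zero or a ratio outside 0 to 1. Its caveat about not being powered is attached to the interactions, not to mediation.

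Elsewhere in section 12.0, the efficacy analysis treats adherence as binary: "Proportion of participants with Clinic attendance (yes/no), ART adherence (yes/no", compared by modified Poisson regression and reported as a relative risk. The sample size paragraph sets the cut at 85% of doses. Table 2 also lists adherence measures that are not binary.

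On size: "The study plans to enroll 60 PLWH randomized to CPT-L or Lifesteps", and "sample size was determined based on pragmatic considerations, rather than formal power analysis".

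**The concern.** A proportion mediated is a ratio of two estimates. When its denominator, the total effect, cannot be told apart from zero, the ratio can take almost any value, including negative values and values above 1. A value that happens to land at 0.7 looks credible and may be just as much noise.

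Avoidant coping is the proposed mechanism in the second exploratory aim (section 1.0), and the mediation paragraph links this work to mechanism testing in the later R01. A single percentage is easily lifted out of a pilot report and quoted without its uncertainty.

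For ART adherence there is a second problem. With the formula and scale unstated, an analyst could choose among definitions that give different answers from the same data.

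**Working it through.** **Inputs from the documents.** 60 randomised, 30 per arm (section 12.0, sample size). Retention of 90% (section 12.0, Data Analysis Aim 2) gives 0.90 × 60 = 54. Retention of 80% (section 1.0, Aim 2 benchmark A) gives 0.80 × 60 = 48.

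**Reproducing the plan's precision.** The half-width of a 95% interval for a mean difference, in SD units, is 1.96 × √(2/n per arm).
- n = 30: 1.96 × √(2/30) = 0.506, matching the stated 0.51 SD.
- n = 27: 0.533. n = 24: 0.566.

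For 10% versus 20% with detectable viral load, the plan says the sample "will provide an 18% confidence interval on either side of the estimated difference". Check: 1.96 × √(0.1×0.9/30 + 0.2×0.8/30) = 1.96 × 0.0913 = 0.179. Viral load is not a mediation outcome, but this is the only between-arm effect the plan illustrates. At 10/9.13 = 1.10 standard errors, the observed difference would have the wrong sign in about 14% of trials.

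So the denominator of the ratio is not separable from zero unless the estimated effect is about half an SD or more.

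**Ratio for a continuous outcome.** Write a for the effect of treatment on the mediator, b for the effect of the mediator on the outcome given treatment, and c′ for the direct effect. The proportion is ab/(ab + c′). It lies outside 0 to 1 exactly when ab and c′ have opposite signs.

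The documents give no values for these paths, so the following are assumed: total effect d of 0, 0.2, 0.35, 0.5 or 0.8 SD; true proportion 0.3, 0.5 or 0.8; a of 0.5 or 0.8 SD; within-arm outcome SD of 1; b = proportion × d/a. The combination d = 0.8, proportion 0.8, a = 0.5 is excluded because b would be 0.64/0.5 = 1.28, more than the outcome SD allows. With 8,000 simulated trials per setting, the estimate fell outside 0 to 1 as follows (range over proportion and a):

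| Total effect (SD) | N = 60 | N = 48 |
|---|---|---|
| 0 | 58–62% | 58–62% |
| 0.2 | 39–50% | 42–53% |
| 0.35 | 24–41% | 28–41% |
| 0.5 | 12–35% | 16–37% |
| 0.8 | 3–17% | 5–20% |

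A percentile bootstrap interval for the ratio (1,000 resamples, 200 trials per setting, N = 60) extended both below 0 and above 1 in about 88% of trials at 0.2 SD, 63–66% at 0.5 SD and 18–22% at 0.8 SD.

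**Ratio for a yes/no outcome, if fitted by logistic regression.** Here the total coefficient c from the model without the mediator does not equal c′ + ab. Take a = 0.8, b = 1.5, c′ = 0.5, control-arm adherence 50% and 400,000 observations:
- ab/(ab + c′) = 1.2/1.7 = 0.71
- ab/c = 0.99, so c is about 1.2/0.99 = 1.21
- 1 − c′/c = 1 − 0.5/1.21 = 0.59
- proportion on the risk-difference scale = 0.68

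Under full mediation with 50–80% control-arm adherence, ab/c was 1.27–1.40 while ab/(ab + c′) was 1.00. At N = 54 or 60, ab/(ab + c′) was outside 0 to 1 in 24–42% of trials and ab/c in 36–57%.

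**The case against.** The case on the other side has real content.

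- **The frequency depends on assumed effects.** The plan states no effect, and at 0.8 SD the ratio is reasonably well behaved. This stands, and the figures must be read as conditional. However, nothing in the documents supports presuming an effect that large, and both arms receive Lifesteps, so adherence is compared against an active adherence session.
- **The yes/no form and the logistic fit are not in the mediation paragraph.** This stands. The binary form is inferred from other parts of section 12.0, and no link is stated. Under a linear fit, c = c′ + ab holds exactly and only the instability remains.
- **A reader might infer that the ratio has no valid meaning for yes/no adherence.** That goes too far. In every setting run, ab/(ab + c′) stayed within about 0.10 of the risk-difference proportion. What is supported is that the quantity is undefined as written and depends on formula and scale.
- **A reader might also infer that 1,000 resamples are too few.** In one simulated 54-person trial, repeating the bootstrap moved the ends of the indirect-effect interval by an SD of 0.012–0.015 against a width of about 0.48, roughly 3%. That is immaterial.
- **The analysis is exploratory.** No feasibility benchmark uses it, nothing says the ratio sizes or gates the R01, and indirect and direct effects are already planned. This stands and limits the consequence. It also means that removing the ratio takes almost nothing away.

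**Conclusion.** The point holds, with conditions. The plan commits to a ratio it does not define, over a denominator that its own figures show is known only to about half an SD. For assumed total effects of 0.2 to 0.5 SD and 48 to 60 participants, the estimate is out of range in roughly 12–53% of trials. It is reasonably stable only near 0.8 SD (about 3–20%). These frequencies come from a simple single-mediator simulation with assumed path values. Adjusting for baseline mediator and outcome (assumed correlation 0.6) barely changes the instability.

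For ART adherence the conclusion is narrower: the scale and formula are unstated, and if the outcome is binary with a logistic fit, the competing definitions disagree whatever the sample size. The documents do not support saying that the ratio is meaningless there, or that it will be out of range often whatever the true effect. The consequence is modest, but so is the cost of correcting it.

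**What to change.** In the mediation paragraph of section 12.0:

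1. Delete the proportion mediated.
2. Report the indirect and direct effects with bootstrap confidence intervals, adjusted for the baseline mediator and the baseline outcome.
3. State the scale for ART adherence. For the yes/no outcome, indirect and direct effects on the risk difference would serve. A continuous version at 3 months would rest on the ACTG self-report with its 4-day recall, because Table 2 schedules the pill-count and refill measures only at baseline, week 4 and week 8. That limitation should be stated if the continuous form is chosen.

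The cost is a change of wording, possibly a little extra programming for the risk-difference effects, and the loss of one exploratory summary number. No new data are needed.

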## 13.0 Provisions to Monitor the Data to Ensure the Safety of Subjects

### DATA SAFETY MONITORING PLAN

The Principal Investigator ([name]), with support from Co-Investigators, will be responsible for monitoring the safety and efficacy of this trial, executing the Data and Safety Monitoring (DSM) plan, and complying with the reporting requirements. Data are randomly inspected weekly and inspected thoroughly on a quarterly basis. [name] will provide a summary of the DSM reports to NIH/NIMH on an annual basis as part of the progress report. All DSM reports will include a brief description of the trial, baseline sociodemographic characteristics, retention rates and disposition of study participants, quality assurance issues, regulatory issues, AEs and SAEs, as well as any actions or changes with respect to the protocol. The DSM report to NIH will also include, when available, the results of any efficacy data analysis conducted.

#### SECTION A. Monitoring Entity.

Considering the study rationale, population, intervention and control procedures, and the risk: benefit profile as outlined, the overall risk level for participation in this study is viewed to be classified as: **Minimum Risk.**

##### DSM Plan Administration

A Data Safety and Monitoring Board (DSMB) will be assembled. The DSMB will act in an advisory capacity to the PI to monitor participant safety, to evaluate the progress of the study, and to review procedures for maintaining the confidentiality of data, the quality of data collection, and data management and analyses. Frequency of meetings of the DSMB will be determined by recruitment milestones (e.g., after 25% of participants have been recruited, etc.), and will follow each SAE report, but meetings will occur no less than once per year. The purpose of these meetings will be to review study progress, data quality, and participant safety.

The DSMB will be made up of professionals with appropriate expertise, who are willing to participate, and who do not have any conflicts of interest. The DSMB will include: 1) one expert in the area of PTSD treatment, 2) one expert in the area of adherence intervention, 3) a statistician with expertise in feasibility measurement, and 4) two members with expertise in the area of HIV care. DSMB membership will be reviewed and approved by the MUSC IRB and NIH. Should there be any questions regarding the independence of the DSMB, it will be addressed and corrected, if necessary, at that time.

##### Conflict of Interest for DSMB

DSMB members will have no direct involvement with the study investigators or intervention (e.g., no portion of their effort will be covered by the study). Each DSMB member will sign a Conflict of Interest statement which includes current affiliations (if any) with pharmaceutical and biotechnology companies (e.g., stockholder, consultant), and any other relationship that could be perceived as a conflict of interest related to the study and/or associated with commercial interests pertinent to study objectives. Data will be presented in a blinded manner during the open sessions of the DSMB. At DSMB meetings, data and discussion are confidential. Participant identities will not be known to the DSMB members.

##### DSMB Responsibilities

The responsibilities of the DSM for this study are as follows:

- Review the research protocol, informed consent documents, and plans for data safety and monitoring;
- Evaluate the progress of the pilot trial, including periodic assessments of data quality and

timeliness, recruitment, participant risk versus benefit, performance of the trial site, and other factors that can affect study outcome;

- Consider factors external to the study when relevant information becomes available, such as scientific or therapeutic developments that may have an impact on the safety of the participants or the ethics of the study;
- Review study performance, make recommendations and assist in the resolution of problems reported by the Principal Investigator;
- Protect the safety of the study participants;
- Make recommendations to the Principal Investigator concerning continuation, termination, or other modifications of the trial based on the observed beneficial or adverse effects of the treatment under study;
- Review interim analyses (The interim data analyses will only include safety related results; analyses in regards to study outcome will not be performed. The interim AE reports will provide typology, frequency data and outcomes of all reported and documented AE in the electronic study database);
- Ensure the confidentiality of the study data and the results of monitoring;
- Assist the PI by commenting on any problems with study conduct, enrollment, sample size, and/or data collection;
- The DSMB will have the authority to temporarily or permanently discontinue the study if it perceives that harm is occurring due to the intervention. The DSMB statistician will evaluate the confidentiality and integrity of the database and the procedures for recording and storing confidential files. The DSMB will also review the elements of the plan to manage emergencies.

## **SECTION B. Procedures for Safety, Risk and Confidentiality**

### **1) Monitoring Study Safety**

From the initial screening of the participant by inclusion and exclusion criteria to the informed consent process to the provision of participant study instruction to staff training in Good Clinical Practices (GCP) and regulations pertaining to the Conduct of Human Participant Research to weekly contact with participants to internal monthly quality control audits and protocol fidelity monitoring to the real-time review of AE by the DSM to the oversight of MUSC's IRB, procedures for monitoring study safety are consistently afforded throughout study. Specific procedures include:

- Participants will be screened for inclusion and exclusion per the protocol; the PI or project coordinator (PC) shall verify 100% of participants' eligibility prior to study enrollment through review of inclusion and exclusion criteria with potential participants.
- Participants will be fully informed as to all known risks and the possibility of risk from study participation in the informed consent process. These risks are minimal.
- Participants will be instructed to notify the researchers of any/all suspected or experienced adverse events whether they believe them to be related or not to the intervention.
- The PI or PC will track all reported participant AEs through to resolution. Please see Section C. 1 – 4.
- All investigators and research staff will maintain active CITI training.
- The PI or PC will maintain weekly contact with all participants to elicit information about AE's and to monitor participant study progress, compliance and safety.
- The PI or PC will review participants study logs for fidelity compliance with the CPT-L and Lifesteps Protocols.
- The PI or PC will conduct a monthly internal quality control audit of all participant records to ensure compliance with MUSC IRB regulations; the PI and PC will work together to correct any errors.
- The PI and/or designee will observe and evaluate ten (10%) percent of eligibility screening visits, informed consents and study instructions performed by IRB approved study personnel and provide feedback and/or retraining of study personnel if fidelity to both applicable federal regulations and the protocol is not observed.
- The DSMB Biostatistician shall generate semi-annual AE reports for the PI and DSMB to review.
- Investigator performance and compliance will be provided for through MUSC IRB and ORI study oversight.

## 2) Minimizing Research-Associated Risk

Diligent study safety monitoring will be conducted by the PI and the study's DSM team throughout the conduct of this study in compliance with the following required elements of MUSC IRB's continuing review process:

1. Tracking and follow-up of participant accrual (inc. withdrawn consents) will minimize risk by identifying, disclosing, and mitigating any potentially unknown risk(s) of harm to study participants. These risks are minimal.
2. Timely and appropriate reporting of informed consent process deficiencies, protocol deviations, privacy breaches, conflicts of interest, and/or changes in personnel.
3. Ongoing soliciting, monitoring and appropriate reporting of adverse event activities.
4. Timely and appropriate IRB submission of safety-related documents such as audit reports, sponsor progress reports, ISM reports, and other materials or communications that might impact the safe conduct of this study.
5. Active cooperation with the IRB, ACO, sponsor, and other applicable entities in the event of a random or for-cause internal or external audit.

## Institution-Wide Assurances

This protocol will be conducted fully in keeping with the signed MUSC IRB Principal Investigator Statement of Assurance and Department Chair's Statement of Assurance, when submitted to the IRB as a required component of the MUSC IRB Human Research Review Application. Assurances include the following safety-related agreements.

## 3) Protecting Confidentiality of Participant data

**Participant Screening and Enrollment.** All data from participants screened for the study will be entered into a REDCap electronic study database. Screened patients who do not meet study eligibility will have specific screening data entered into this database. The collected data will be helpful in examining the patient population and feasibility of enrollment criteria and will include reason for exclusion. PHI will be immediately stripped from this database for screen failures or for those participants who do not consent or are enrolled into the study. For participant enrolled into the study, dates will be shifted and other Personal Health Information (PHI) will be removed upon completion of the study. All data obtained from this study will be used for research purposes only and will comply with Federal HIPAA regulations. Master Screening and Enrollment Logs will be maintained electronically and will only be accessible to be used by the PIs or PC in preparation of reports on accrual and attrition for the DSMB.

**Electronic Case Report Forms.** All proposed study specific case report forms (source documents) for data collection will be designed by the PI and transferred by the PI or PC into electronic Case Report Forms (eCRFs) for use in the study's REDCap database. These study specific eCRFs source documents (study logs for correspondence, compensation and other forms such as pre-eligibility screens) will be coded by the participant's unique study ID# for all data collected including study instruments and will be maintained in the participant's unique electronic research record.

**Regulatory Binders.** The MUSC PI and/or designee will prepare and maintain an electronic regulatory file to include the IRB-approved protocol, IRB correspondence, approved study advertising, and other required study-related regulatory documents.

**Data Processing.** This study will use Research Electronic Data Capture (REDCap) for data capture and management. REDCap is a software toolset and workflow methodology for the electronic collection and management of research and clinical trials data. REDCap provides secure, web-based, flexible applications, including real-time validation rules with automated data type and range checks at the time of data entry. Exports are made available for several statistical packages including SPSS, SAS, SATA, R and Microsoft Excel. The study-specific REDCap electronic database will be designed and developed by the PI or PC in concert with the biostatistician. The provision of REDCap is made available through the South Carolina Clinical & Translational Research (SCTR) Institute at MUSC with NIH Grant awards UL1RR029882 and UL1TR000062.

**Data Security.** Ensuring data security, compliance with 45 CFR 46 and maintaining the integrity of PHI is a top priority. MUSC has Standard Operating Procedures (SOP) to ensure a high level of data security while coordinating electronic and paper data management activities for clinical research trials. The REDCap study database will be hosted in the Biomedical Informatics secure data center at MUSC, a secure environment for data systems and servers on campus, and includes firewall, redundancy, failover capability, backups and extensive security checks. The secure data center has strict access control; only authorized core personnel may access the facility un-escorted. Only authorized users are allowed to connect to the network, and the security of the network is actively monitored. Power and environmental controls have several layers of backups, from interruptible power supplies to alternate and redundant feeds to the local utility company. The REDCap system administrator contributes to the maintenance of institutional disaster recovery and business continuity plans. Load balancers and a highly fault tolerant SAN infrastructure contribute to high availability.

The REDCap system itself has several additional layers of protection including password protection. Access to the data and its security is managed institutionally by sponsored login IDs through a Shibboleth login with an MUSC issued NetID and features a user account management filter that controls who can access the data and to what degree. All personnel must pass an employment background check before being issued an ID. Password complexity, history and expiration standards are implemented at the institutional level. Access to individual REDCap projects and their data is managed by the owner of the project. All transactions are securely delivered to the application using Secure Sockets Layer (SSL – SHA-1 with RSA Encryption; 2048-bits). It is then transmitted internally (behind the firewall) to the database server. All transactions are logged at the server layer (httpd logging), application layers (REDCap logs activity to a database table), and the database layer, using both query and binary logging. This feature provides audit trails for all changes, queries, data exports and reports. MUSC Information security policies are available at: <https://mainweb-v.musc.edu/security/policy/>

**Data Entry.** Only MUSC IRB approved study personnel that are authorized to have access to the REDCap study database will be granted password access. Study personnel using computers that are connected to the Internet will directly enter data into the remotely housed database. As such, no electronic study data will be stored on hard drives and/or any portable electronic devices. Additionally, all personnel with access to the database will have current University of Miami CITI training in the Conduct of Human Subject Protections, and HIPAA and Information Security trainings that are completed annually. Each participant will be assigned a unique study identifier, all PHIs will be masked, and data exports will be limited to the PIs, the PC, or the project biostatistician for generating reports and the conduct of statistical data analysis.

**Data Monitoring.** Ongoing quality control procedures will be implemented for data collection, storage and processing. The PI or PC will conduct monthly monitoring of the study database and generate a report for review at team meetings. Standing agenda items for these meetings will include participant recruitment and retention, AE's, protocol deviations, data integrity and overall study conduct. The PI and PC will work to resolve and validate discrepant data. Discrepancies that warrant clarification will be sent to appropriate parties for review and resolution. All data entry and changes made in the study database by authorized study personnel will be automatically logged by REDCap, and provide a transparent visible audit trail for reviewers.

